Primary: Disease control rate at 24 weeks after initiation of tamoxifen (since day 1 cycle 1), defined by absence of radiological progression in conventional imaging

examinations by RECIST 1.1 (Appendix I). Isolated increase of biomarker (chromogranin A) or specific hormone will not be considered progression.

Secondary:

(1) Progression-free survival, defined by time from tamoxifen day 1 cycle 1 to death from any cause or radiological progression by RECIST 1.1, whichever occurs first. Patients alive and without progression at the time of study analysis will be censored for time-to-event analysis.

(2) Biochemical response will be defined by at least 30 percent drop in the marker (chromogranin and / or specific hormone) at any time of treatment in relation to pre-treatment value (s).

(3) Radiological response rate by RECIST criteria 1.1 during the study period.

(4) Disease control rate, defined by absence of radiological progression by RECIST 1.1 criteria, according to the intensity of expression by immunohistochemistry (IHC) of HR and also according to primary site (pancreas, gastrointestinal or lung) during the study period.

(5) Toxicities frequency: Adverse events of grades 2 or more by Common Adverse Event Toxicity Criteria (CTCAE) version 5.0 during the study period.

Exploratory:

(1) Evaluate possible variations in intensity and number of sites between PET-CT gallium-68 pre-treatment and 12 weeks after initiation of tamoxifen as a continuous variable for each capture lesion. Although this examination is part of the evaluation routine of NET, in this study we will evaluate differences in the intensity of uptake with tamoxifen.

(2) Evaluate the percentage of CTC positivity in NET, as well as average number of cells in case of positivity. To evaluate the presence of estrogen and progesterone receptors in CTC.

Methodology:

Study design:

A single-arm, unicentric, single-stage clinical study of tamoxifen for patients with well differentiated neuroendocrine tumors and radiological progression with positive (> 1 percent) HR (estrogen and / or progesterone) expression by IHC.

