Descriptive statistics will be used to report the results of categorical and continuous variables. The time-to-event variables will be reported in medians and Kaplan Meyer curves. The degrees of toxicity will be tabulated. The number of patients discontinuing treatment due to toxicity will be presented.

Efficacy and toxicity analyzes will be performed by intention to treat. Patients receiving at least one dose of tamoxifen will be evaluated for toxicity and efficacy.

Inferential analyzes of the primary outcome according to primary site and IHC HR expression intensity will be conducted to depend on the number of cases per subgroup; if possible, these analyzes will be performed with the chi-square test. The analyzes of intensity of uptake intensity to PET-CT gallium-68 will be with paired T-test. The CTC analysis will be presented in a descriptive way.

Sample Size Calculation

To calculate the sample size, we considered the disease control rate H0 at 6 months of 50 percent (placebo arm result of the phase III studies) 5,23 and H1 as a 6 months disease control rate of 70 percent. A 10 percent bitailed type I error was considered, 80 percent power loss and 30 percent follow up loss. With these calculations, the sample number will be 22 patients.

Recruitment and Study Duration

At the AC Camargo Cancer Center, 30 patients with advanced NET are treated annually. Therefore, considering the patients already under treatment and the possible candidates without previous treatment and that out of every 10 patients, N = 4 will meet eligibility criteria (NETs with positive HR), we estimate to recruit the study population in a maximum period of 3 years and have the first full evaluation in 3 ½ years.

Ethical Considerations

The study will be conducted in accordance with the protocol, Good Clinical Practice guidelines of the International Conference on Harmonization (ICH GCP) and applicable local laws and regulatory requirements. The Free and Informed Consent Term (ICF) must be in accordance with ICH GCP guidelines, local regulatory regulations, and legal requirements. See Appendix 2 for ICF.

The investigator should ensure that each study patient, or his / her legal representative, is fully informed about the nature and objectives of the study and

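### The plan lists 30% loss to follow-up and analyses every dosed patient, but never says how a patient without a week-24 image counts; at 30% loss no reading checked gives both the stated power and the stated error rate

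*Combined protocol and SAP*

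**What the plan says.** The primary outcome is the disease control rate 24 weeks after the first dose, "defined by absence of radiological progression in conventional imaging" by RECIST 1.1 (Outcomes, Primary).

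Under Sample Size Calculation, the null rate is 50%, taken from the placebo arms of earlier phase III trials. The alternative is given as "H1 as a 6 months disease control rate of 70 percent". The type I error is 10%, two-sided. Power and loss appear together in the phrase "80 percent power loss and 30 percent follow up loss", whose garbled first half I read as 80% power. The paragraph closes with the resulting figure: "With these calculations, the sample number will be 22 patients".

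Under Statistical plan: "Efficacy and toxicity analyzes will be performed by intention to treat". The sentence after it extends both evaluations to anyone who has taken at least one dose.

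The only censoring rules concern progression-free survival: the secondary outcome definition, and the Efficacy and Follow-Up Assessment section on starting a new treatment. Neither applies to the binary primary endpoint. No section says whether a dosed patient with no week-24 image is a failure, a success, excluded or imputed, and no test or success threshold is named for the overall primary rate.

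**The concern.** The 50% and 70% rates describe patients whose week-24 status is known. The analysis set is all dosed patients, and the plan allows for 30% of them being lost. If those patients stay in the denominator of a simple proportion, they must be given a status, and that choice moves the analysed rate away from 50% and 70%. The plan does not make the choice.

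Counting losses as failures can pull a truly active drug down to the null. Counting them as controlled, which the wording about absence of progression would allow, can push an inactive drug above it. In a single-arm study with no comparator, an unstated rule could also be settled after the data are seen.

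**Working it through.** **Inputs.** From Sample Size Calculation: p0 = 0.50, p1 = 0.70, two-sided alpha 10% (5% in the upper tail), power 80%, loss d = 0.30, N = 22. My assumptions: loss is independent of outcome; the test is exact binomial, one arm, upper tail at most 5%.

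**1. The plan's own figure.**

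n = [(z(0.95)·√(p0(1−p0)) + z(0.80)·√(p1(1−p1))) / (p1−p0)]²
= [(1.645 × 0.500 + 0.842 × 0.458) / 0.20]² = 36.5, so 37 evaluable patients.

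The exact test agrees: 24 of 37, tail 4.9%, power 80.7%. With 30% loss, 37 / 0.70 = 52.9, so 53 enrolled. The stated 22 is not reproduced, and how the 30% entered it cannot be recovered.

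**2. Test at N = 22.** The smallest k with P(X ≥ k | 22, 0.50) ≤ 0.05 is 16 (tail 2.6%). With full follow-up, P(X ≥ 16 | 22, 0.70) = 49.4%.

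**3. Analysed rate under loss.** If a share f of lost patients counts as controlled, the rate is p(1−d) + f·d.

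| Rule at 30% loss | H0 rate | H1 rate |
|---|---|---|
| Lost = not controlled (f = 0) | 0.50 × 0.70 = 35% | 0.70 × 0.70 = 49% |
| Lost = controlled (f = 1) | 0.35 + 0.30 = 65% | 0.49 + 0.30 = 79% |

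**4. Lost = not controlled.** Power at N = 22, success at 16 or more:

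| Loss | H1 rate | Power |
|---|---|---|
| 0% | 70% | 49.4% |
| 10% | 63% | 23.8% |
| 20% | 56% | 8.4% |
| 30% | 49% | 2.1% |

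At 30% loss a larger N does not help: power is 3.8% at N = 37 and 3.6% at N = 53. A rate below 50% cannot pass an upper-tail 5% test against 50% more than 5% of the time at any N. The H1 rate meets the null where 0.70(1−d) = 0.50, that is d = 28.6%. At lower loss the same rule is workable: about 55 patients give 80% power at 5% loss, and about 90 at 10% loss.

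**5. Lost = controlled.** If all losses come before any follow-up scan, the false-positive rate is P(X ≥ 16 | 22, 0.65) = 30.2%. Power is then P(X ≥ 16 | 22, 0.79) = 83.9%, so that reading reaches 80% power only by giving up the error rate. If losses are spread evenly over 24 weeks and progression seen at week 12 still counts, simulation gives a false-positive rate of about 17% (40,000 trials, exponential progression, scans at weeks 12 and 24).

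**6. Lost = excluded.** About 22 × 0.70 = 15 patients remain. The cut is 12 of 15 and power is 30%.

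**7. Kaplan-Meier at 24 weeks, all dosed patients, losses censored at the last scan.** Same simulation, with success if the one-sided 95% log-log lower bound exceeds 50%: upper-tail error 3.5%, power about 42% to 43% at N = 22.

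**The case against.** **The 49% is conditional.** A reader might infer that the plan's intention-to-treat rate under H1 is 49%. The documents do not support that. They say who is analysed, not how a missing image is scored; 49% needs a missing-equals-failure rule that appears nowhere. The possible range is 49% to 79%. For the same reason one cannot say that this plan would almost always reject an active drug: that needs the failure rule, a loss of about 30%, and a threshold of 16 of 22 that is mine.

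**A loss allowance and an all-dosed analysis can coexist.** It is tempting to say that a loss allowance is valid only in completers. It is not: with censoring, every dosed patient stays in and the loss costs only precision. Nor do the documents show that 22 was reached by removing lost patients.

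**Much of the shortfall is the sample size.** Power is 49% before any loss. That is a separate error, and correcting it does not settle this one: 53 patients still have 3.6% power under the failure rule at 30% loss.

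**30% is an allowance, not a forecast.** Imaging is routine care at the centre, and patients who stop for clinical progression may continue to be scanned. Actual loss may be lower.

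**The 30% false-positive figure is an extreme.** Appendix 1 requires stable disease to be documented at least once more than 4 weeks from baseline, which argues against counting a patient with no follow-up scan as controlled. The 17% figure is the more realistic one. Appendix 1 also assigns response categories after at least one cycle rather than one dose, so it does not settle the analysis set.

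**Kaplan-Meier is not neutral.** If 50% of progressors and 10% of non-progressors were lost under H0 (30% overall, an assumption), its upper-tail error would be about 16% to 17%.

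All of this stands as a limit on the claim. None of it supplies the missing rule.

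**Conclusion.** The point holds in conditional form. The plan combines undiluted rates, a 30% loss allowance and an analysis of all dosed patients without a rule for the missing week-24 assessment. This is more than a missing detail, because at the plan's own loss figure with 22 patients none of the four readings checked gives both 80% power and a 5% upper tail:

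- failures: 2.1% power;
- controlled: about 17% to 30% false positives;
- excluded: 30% power;
- Kaplan-Meier: about 42% to 43% power with 3.5% error.

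These figures rest on loss independent of outcome and an assumed upper-tail 5% test (exact binomial for the counts, log-log bound for Kaplan-Meier). The simulated figures also assume exponential progression, losses spread evenly over 24 weeks, and scans at weeks 12 and 24. The documents do not establish which reading the sponsor intends.

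**What to change.** In Statistical Considerations, name one rule for the primary analysis before the data are examined. A suitable one:

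1. Estimate 24-week disease control by Kaplan-Meier in all patients with at least one dose. Radiological progression and death are events; lost patients are censored at their last evaluable scan. Death is not in the current primary definition, so that definition needs the same edit.
2. Read the curve at the end of the week-24 imaging window, so that late scans count. The efficacy section allows ±5 days for imaging and Table 1 shows ±3; state which applies.
3. Compare the 90% log-log confidence interval with 50%.
4. Report the count with lost patients as not controlled as a sensitivity analysis, because Kaplan-Meier assumes that loss is unrelated to progression.
5. Replace the 80% power claim with the power and type I error of the chosen rule at 30% loss: for Kaplan-Meier at N = 22, about 42% to 43% and 3.5%.

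If the sponsor prefers a simple proportion with losses as failures, the plan should state that H1 is 49% on that scale at 30% loss, and that 80% power is then out of reach at any N.

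The cost is wording and a short recalculation, with no added patients, scans or visits; Kaplan-Meier is already planned for the time-to-event outcomes. The price is a less favourable stated power and reliance on the loss assumption. The rule does not repair the sample size, which needs its own correction.

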Tamoxifen Citrate was the first selective modulator of the developed estrogen receptor. It is a prodrug that has, in itself, little affinity for its target protein, the estrogen receptor. Tamoxifen is metabolised in the liver by the CYP2D6 and CYP3A4 isoforms of cytochrome P450 in its active metabolites afimoxifene and endoxifen, which present 30-100 times more affinity for the estrogen receptor. These active metabolites compete with estrogen for the body binding to the estrogen receptor, possessing 178 percent and 338 percent more affinity for estrogen and alpha receptors, respectively, than estradiol. They have different activities depending on the target tissue. In mammary tissue, they act as receptor antagonists. In other tissues, such as the endometrium, it is agonist. Because of this variable activity, tamoxifen is considered a selective modulator of the estrogen receptor. In hormone receptor-positive breast cancer tumor cells, active metabolites bind to the receptor producing a nuclear complex that decreases DNA synthesis by modulating gene expression, inhibiting estrogenic proliferative effects. The antitumor effect occurs by maintaining the cells in the G0 and G1 phases of the cell cycle, therefore, being a cytostatic rather than cytotoxic agent. Since the demonstration of antineoplastic activity in breast cancer in clinical studies in 1971, tamoxifen has become the prototype drug for

hormone treatment of breast cancer patients positive for hormone receptors at all stages of the disease, both pre- and post- menopause.²¹

The metabolism of tamoxifen is complex (about 10 major metabolites have been identified) and is mediated in the liver by cytochrome P450. Metabolites are excreted mainly by bile. The initial plasma half-life of tamoxifen ranges from 4 to 14 hours, with a secondary half-life of approximately 7 days. The concentration stability of tamoxifen is reached after 4 to 16 weeks of treatment. This prolonged half-life reflects levels of plasma protein binding and enterohepatic recirculation. There is no need for adjustment for renal function and has not been studied in patients with severe hepatic dysfunction.

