The main adverse effects of tamoxifen are hot flushes, dry skin, nausea, vaginal discharge, fatigue and changes in the menstrual cycle. Rarely, but importantly may be associated with retinal changes, hepatotoxicity, hematological changes, thromboembolic phenomena and endometrial neoplasia. Given the teratogenic potential, women of childbearing potential should undertake contraceptive measures. Such medication should be contraindicated in cases of hypersensitivity to tamoxifen or any component of the formulation, concomitant use of coumarins and history of deep vein thrombosis or pulmonary embolism.

Administration

The treatment to be used will be tamoxifen 20mg VO once daily with a glass of water. In cases of vomiting occurring after 1 hour of taking or when a dose is missed, the patient will be instructed to skip this dose and not compensate for the next dose. Each cycle will be defined for 42 days (6 weeks).

Aderence:

The dispensation of tamoxifen will be made by the research pharmacy of the institution. Approximately 20 mg tamoxifen tablets will be given to each patient until the next return to the oncologist (see TABLE 1).

To assess adherence to treatment we will require patients to bring the blisters at each visit and at the time of discontinuation of treatment.

Dose reduction:

Dose interruption or reduction will be allowed in case of any toxicity of degree equal to or greater than 3 or intolerable grade 2 toxicity, as shown in the table below.

TABLE 3 - Dose adjustment according to toxicity

Study drug and dose	Tamoxifen 20mg orally once daily
Haematological or non-haematological toxicity grade \geq 3 or grade 2 intolerable.	Suspend therapy until recovery of the condition (with weekly evaluation by the investigator until the end of the recovery). When improvement of the picture (grade 1 toxicity), restart with tamoxifen 10mg tablet orally daily If there is no improvement in clinical status within 3 weeks (persisting with grade 3 or grade 2 intolerable toxicity) or patient does not tolerate the 10 mg / day dose, the patient will be excluded from the study for unacceptable toxicity.
Haematological or non-haematological toxicity <grade 2	No dose reduction will be performed for tolerable grade 1/2 toxicities.

Security Assessment

Baseline Assessment:

After signing the informed consent form, patients will be submitted to baseline evaluation to assess the patient's eligibility (see TABLE 1):

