- Within 21 days of the first dose of treatment: investigation of the immunohistochemical expression of RH in the paraffin-shaped tumor material. If expression \geq 1 percent, eligibility is confirmed and the following procedures are:

- Within 3 days of day 1 cycle 1: Medical history, including diagnosis and previous treatments, history of other diseases (active and resolved), medications in use and general demographic data. Complete physical examination, ECOG (PS) performance index, body weight and height, and vital signs.
- Laboratory tests: blood count, urea, creatinine, ALT, AST, total bilirubin, sodium, potassium, INR and albumin and pregnancy test for women of childbearing age will be performed within 3 days of the first dose of treatment; these patients will be directed to contraception.
- It will be accepted that baseline imaging has been performed within 8 weeks of the first dose of treatment: Computed tomography (or nuclear magnetic resonance, if applicable) of the abdomen, pelvis and chest.
- All of these above exams are already part of the routine in treating NET at the AC Camargo Cancer Center.

Security Assessment at Week 3:

Adherence and presence of adverse events will be assessed at this time (see Safety Assessment). Will be allowed window of +/- 5 days

Safety evaluation on other weeks:

At each medical appointment, the adverse effects and toxicity related to the treatment will be evaluated by means of anamnesis, physical examination and laboratory evaluation, as follows:

- Complete physical examination, measurement of vital signs, measurement of weight and height, ECOG, use of concomitant medications.
- Evaluation of adherence to treatment.
- Evaluation of adverse events

- Laboratory evaluation: blood count, urea, creatinine, ALT, AST, total bilirubin, sodium, potassium, and others, if clinically indicated.

To grade toxicities, we will use CTCAE 5.0 criteria. Patients who present intolerable grade 2 toxicity or grade 3 that the investigator judges to be related to tamoxifen will have the reduced dose of treatment (see TABLE 3) and will be conducted as previously discussed. All adverse effects will be graded and evaluated whether or not they are related to treatment.

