If there is no CTCAE 5.0 classification for an adverse event, the severity degree of mild, moderate, severe and life threatening will be used. Adverse event monitoring will be performed at Week 3 after initiation of treatment (window - / + 3 days) and at each return with the oncologist every 6 weeks (window - / + 3 days). Monitoring of adverse events should be continued for at least 4 weeks after the last dose of study treatment.

An adverse event for the purposes of this protocol is the appearance of (or worsening of the pre-existing) signal (s), symptom (s) or undesirable medical condition (s) occurring after signature of free and informed consent, even if the event is not considered to be related to the study drug (s). The occurrence of adverse events should be obtained through indirect questions asked to the patient at each visit during the study. Adverse events may also be detected when reported voluntarily by the patient during or between visits or by physical examination, laboratory examination or other evaluation.

Whenever possible, each adverse event should be evaluated to determine:

1. Severity (mild, moderate, severe and life threatening) or (CTCAE grade 5.0)
2. Their relationship to each study drug (suspected / suspected)
3. Their duration (starting dates and final or continuing in the final exam)
4. Conduct adopted (no dosage adopted, dosage of study drug adjusted / temporarily discontinued, study drug permanently discontinued as a result of said adverse event, concomitant medication given, non-medicated therapy, prolonged hospitalization / hospitalization).

Patients requiring hospitalization should be immediately identified by the study investigators who monitor all patients.

Treatment suspension criteria:

Patients can discontinue study treatment for one or more of the following reasons:

- Progression of the disease (documented by images and defined by RECIST 1.1 criteria)

Clinical progression, based on the evaluation of the investigator

- Death.
- Adverse event
- Withdrawal of consent by the patient.
- Need for new cancer therapy and / or surgery.

Efficacy and Follow-Up Assessment

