For evaluation of efficacy, patients will perform imaging (chest tomography, abdomen and pelvis or abdominal and pelvic resonance) at baseline and every 12 weeks until progression or intolerance. Patients will also be evaluated for signs and symptoms that may be related to disease progression. Patients who present clinical progression at the investigator's judgment, but without radiological progression, may discontinue treatment with tamoxifen and continue imaging until progression; however, if new treatment is instituted, the last date of receipt of tamoxifen will be the date of censure in the analysis of progression-free survival.

Patients will also be evaluated for somatostatin receptor expressiveness through the functional examination of PET-CT Gallium-68, which will be performed before treatment and at week 12, in addition to biochemical response through the dosage of chromogranin A and / or specific hormone every 12 weeks, in conjunction with imaging (tomography and / or resonance). An interval of +/- 5 days will be

allowed for imaging and PET-CT Gallium-68 exams. Patients with suspected progression (eg worsening of symptoms) may perform images within less than 12 weeks to assess progression of disease, at the discretion of the investigator.

After documentation of progression or exit from the study for other reasons, patients will be followed up by the investigator or other oncologist from the Clinical Oncology team for symptom control, imaging monitoring and possible future therapies. The patient continues to be cared for at the AC Camargo Cancer Center, if desired.

Other concomitant medications

In general, concomitant medications and therapies deemed necessary for the intensive treatment and safety of the patient are permitted provided that their use is documented in the patient's records and in the appropriate clinical record. Tamoxifen may have drug interaction with coumarin anticoagulants (Marcoumar, Marevan, Coumadin) and those with some of the new anticoagulants (Pradaxa, Xarelto). These drugs should be avoided during the study (moderate contraindication). Concomitant administration of investigational medicinal products is not permitted. Administration of any other anticancer agents including chemotherapy, target therapy and biological agents is not permitted.

Statistical Considerations

Statistical plan

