possible risks associated with participation. The investigator will obtain the written consent of each patient before any specific study activity is performed. The investigator will retain one path of each consent form signed by the patient. It will be emphasized that participation is voluntary and that the patient has the right to refuse participation or to leave in the middle of the study whenever he wishes. This will not impair subsequent care to the patient. Female patients will be instructed not to become pregnant during treatment, being advised to use contraception methods if they are of childbearing age, as already done in routine. There is a risk of loss of confidentiality if patient data are identified, however, all appropriate measures will be taken to prevent this from happening.

The protocol was approved by the Local Ethics Committee (Registration Number: 2626/18). The study will be enrolled in the ClinicalTrial.gov international clinical trial bank.

Funding and Sponsorship of the Study

The patient will not incur any costs in relation to the immunohistochemical test for HR or use of tamoxifen to be funded by development. All the rest (laboratory tests, hormonal dosages, conventional imaging tests, gallium-68 PET-CT, medical consultations) is not part of this protocol because it is already part of the routine treatment of NET patients in the AC Camargo Cancer Center and therefore, paid by the paying source. For this study, insurance will be contracted against risks of adverse events requiring medical intervention (complementary examinations, hospitalization or emergency passage of AC Camargo due to adverse events related to tamoxifen)

References:

- 1.Yao, J. C. et al. One hundred years after 'carcinoid': epidemiology of and prognostic factors for neuroendocrine tumors in 35,825 cases in the United States. *J. Clin. Oncol.* **26**, 3063–3072 (2008).
- 2.Caplin, M. E. et al. Carcinoid tumour. *Lancet* **352**, 799–805 (1998).

3. Modlin, I. M., Pavel, M., Kidd, M. & Gustafsson, B. I. Somatostatin analogues in the treatment of gastroenteropancreatic neuroendocrine (carcinoid) tumours. *Aliment. Pharmacol. Ther.* **31**, 169–188 (2010).
4. Caplin, M. E. et al. Lanreotide in metastatic enteropancreatic neuroendocrine tumors. *N. Engl. J. Med.* **371**, 224–233 (2014).

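### The pregnancy-avoidance instruction in Ethical Considerations covers only the treatment period, although the protocol's own 7-day half-life leaves about 25% of the drug 2 weeks after the last dose

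*Combined protocol and SAP*

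**What the plan says.** Ethical Considerations ties the instruction to the treatment period: "Female patients will be instructed not to become pregnant during treatment, being advised to use contraception methods if they are of childbearing age". The sentence ends by saying that this matches current routine, but no routine interval is described.

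Two other places deal with contraception, and neither gives an end date. The tamoxifen section says: "Given the teratogenic potential, women of childbearing potential should undertake contraceptive measures". The Baseline Assessment, after the pre-treatment pregnancy test, says: "these patients will be directed to contraception".

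The pharmacology is in the tamoxifen section: "The initial plasma half-life of tamoxifen ranges from 4 to 14 hours, with a secondary half-life of approximately 7 days", and "The concentration stability of tamoxifen is reached after 4 to 16 weeks of treatment".

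Only two provisions reach past the last tablet. Adverse event monitoring under Security Assessment continues: "Monitoring of adverse events should be continued for at least 4 weeks after the last dose of study treatment". Efficacy and Follow-Up Assessment keeps patients in oncology care: "After documentation of progression or exit from the study for other reasons, patients will be followed up by the investigator or other oncologist". Neither mentions contraception or asks for a pregnancy to be recorded. For the consent form, Ethical Considerations refers the reader elsewhere: "See Appendix 2 for ICF". That appendix was not available.

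**The concern.** The protocol calls the drug teratogenic and describes slow elimination, yet the only period it attaches to avoiding pregnancy ends with treatment. An investigator who follows that sentence as written could regard the precaution as finished at the last tablet, while drug is still circulating.

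The situation can arise. Adults from 18 years are eligible, and only pregnant or lactating women are excluded on this ground. The pregnancy test in Table 1 is at screening only. Treatment may stop for toxicity or withdrawal of consent, and patients suitable for watchful waiting may enrol. A woman can therefore stop tamoxifen without starting another therapy that would itself prompt contraception.

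What is at stake is maternal and fetal safety.

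**Working it through.** The documents give no residual-drug or washout figure, so there is nothing to reproduce. The check asks how much drug the stated half-life leaves once the instruction has ended.

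**Inputs (tamoxifen section):** secondary half-life h of about 7 days; initial half-life 4 to 14 hours.

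**Formula:** with first-order decline, the fraction remaining t days after the last dose is 0.5^(t/h).

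**Single 7-day phase:**

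| Time after last dose | Calculation | Remaining |
|---|---|---|
| 2 weeks | 0.5^(14/7) = 0.5^2 | 25% |
| 4 weeks | 0.5^(28/7) = 0.5^4 | 6.25% |
| 5 weeks | 0.5^(35/7) = 0.5^5 | 3.1% |

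**Allowing for the fast phase:** the table assumes that all of the level at the last dose declines with the 7-day half-life. Suppose instead that only a share A does so, and the rest follows the fast phase. The documents do not give A, so the values below are assumptions. Even at the slower 14-hour end, 2 weeks is 336/14 = 24 fast half-lives, so the fast part is negligible and the remainder is A × 0.5^(t/7).

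| Share A | 2 weeks | 4 weeks |
|---|---|---|
| 1.00 | 25% | 6.25% |
| 0.75 | 18.75% | 4.7% |
| 0.50 | 12.5% | 3.1% |

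The amount depends on A. In each case some drug remains at 2 weeks and at 4 weeks.

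**Length of an added interval:** five half-lives is 5 × 7 = 35 days, or 5 weeks. The multiple of five is a convention and does not come from the documents. The 4-week minimum for adverse event monitoring is one week shorter.

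**The case against.** The strongest reply is that the governing text may be elsewhere. The sentence stands in a paragraph about informed consent, and the form in Appendix 2 is what tells women what to do and for how long. It may give a post-treatment interval, and so may the routine practice that the sentence invokes. The other two contraception directions have no end date, and nothing instructs anyone to stop contraception at the last dose. This stands as a limit on the claim: a reader might infer that the plan has no post-treatment contraception interval at all, and the documents do not support that. It does not remove the point, because the sentence still states a period that is too short. If the consent form gives a longer one, the two should agree.

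A reader might also infer much greater persistence from the 4 to 16 weeks to stable levels. If steady state is taken to need 4 to 5 half-lives, those times imply half-lives from 28/5 = 5.6 days to 112/4 = 28 days, and so 18% to 71% remaining at 2 weeks. That range depends on an outside convention and takes one end from each version of it. Its upper end uses a half-life four times the stated 7 days. It should not be presented as the protocol's figure, and it does not justify prescribing a 16-week interval.

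Finally, few women may be affected. The planned sample is 22 patients, and the number of women of childbearing age is not given. That is a fair reason for low priority.

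**Conclusion.** The point holds as a low-priority safety correction, a cheap improvement. The period stated in Ethical Considerations is too short against the protocol's own pharmacology: about 25% of drug at 2 weeks, 6% at 4 weeks and 3% at 5 weeks on a single 7-day phase, or 12.5% at 2 weeks and 3% at 4 weeks if half of the level is in the fast phase.

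These figures assume first-order decline and describe plasma drug. They do not quantify fetal risk: the documents give no half-life for the active metabolites and no exposure threshold, so the required length of contraception cannot be derived from them. The finding is confined to the protocol body and says nothing about what the consent form contains. It has no bearing on the endpoint, the analysis or the sample size.

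**What to change.** 1. In Ethical Considerations, extend the instruction to read: *during treatment and for at least 5 weeks after the last dose*. If the consent form or the sponsor's drug information gives a longer interval, use that instead.
2. Check Appendix 2 and make it state the same interval.
3. In the adverse event monitoring text under Security Assessment, add that any pregnancy beginning within the interval is recorded in the safety data. With 5 weeks, this runs one week past the present 4-week minimum.

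The open-ended contraception directions in the tamoxifen section and the Baseline Assessment can stay as they are.

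The cost is two short edits to the protocol, aligned consent text if it does not already match, and about 5 more weeks of contraception and pregnancy reporting for a probably small number of women.
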